8.1 Adverse events

8.1.1 Definitions and reporting

An adverse event is defined as the appearance of (or worsening of any pre-existing) undesirable sign(s), symptom(s), or medical condition(s) that occur after patient's signed informed consent has been obtained.

Abnormal laboratory values or test results occurring after informed consent constitute adverse events only if they induce clinical signs or symptoms, are considered clinically significant, require therapy (e.g., hematologic abnormality that requires transfusion or hematological stem cell support), or require changes in study medication(s).

Adverse events that begin or worsen after informed consent should be recorded in the Adverse Events CRF. Conditions that were already present at the time of informed consent should be recorded in the Medical History page of the patient's CRF. Adverse event monitoring should be continued for at least 30 days following the last dose of study treatment. Adverse events (including lab abnormalities that constitute AEs) should be described using a diagnosis whenever possible, rather than individual underlying signs and symptoms. When a clear diagnosis cannot be identified, each sign or symptom should be reported as a separate Adverse Event.

Adverse events will be assessed and graded according to the Common Terminology Criteria for Adverse Events (CTCAE) version 4.03. Grade 1 to 5 will be used to characterize the severity of the Adverse Event.

If CTCAE grading does not exist for an adverse event, the severity of mild, moderate, severe, life-threatening, and death related to the AE corresponding respectively to Grades 1 - 5, will be used. Information about any deaths (related to an Adverse Event or not) will also be collected through a Death form.

The occurrence of adverse events should be sought by non-directive questioning of the patient during the screening process after signing informed consent and at each visit during the study. Adverse events also may be detected when they are volunteered by the patient during the screening process or between visits, or through physical examination, laboratory test, or other assessments. As far as possible, each adverse event should be evaluated to determine:

1. The severity grade (CTCAE Grade 1-5)
2. Its duration (Start and end dates)

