3. Its relationship to the study treatment (Reasonable possibility that AE is related: No, Yes) or its relationship to the study treatment (Reasonable possibility that AE is related: No, Yes, investigational treatment, Yes, the study treatment (non-investigational), Yes, both and/or indistinguishable)
4. Action taken with respect to study or investigational treatment (none, dose adjusted, temporarily interrupted, permanently discontinued, unknown, not applicable)
5. Whether medication or therapy taken (no concomitant medication/non-drug therapy, concomitant medication/non-drug therapy)
6. Outcome (not recovered/not resolved, recovered/resolved, recovering/resolving, recovered/resolved with sequelae, fatal, unknown)
7. Whether it is serious, where a serious adverse event (SAE) is defined as in [Section 8.2](#).

If the event worsens the event should be reported a second time in the CRF noting the start date when the event worsens in toxicity. For grade 3 and 4 adverse events only, if improvement to a lower grade is determined a new entry for this event should be reported in the CRF noting the start date when the event improved from having been Grade 3 or Grade 4.

All adverse events should be treated appropriately. If a concomitant medication or non-drug therapy is given, this action should be recorded on the Adverse Event CRF.

Once an adverse event is detected, it should be followed until its resolution or until it is judged to be permanent, and assessment should be made at each visit (or more frequently, if

necessary) of any changes in severity, the suspected relationship to the study treatment, the interventions required to treat it, and the outcome.

All patients who have AEs, whether considered associated with the use of the investigational product or not, must be monitored to determine the outcome. The clinical course of the AE will be followed up according to accepted standards of medical practice, even after the end of the period of observation, until a satisfactory explanation is found or the investigator considers it medically justifiable to terminate follow-up. Should the AE result in death, a full pathologist's report should be supplied if and when available.

SAEs must be reported as outlined in [Section 8.2.2](#). In addition, any SAEs which occur as a result of protocol specific diagnostic procedures or interventions must also be reported.

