10.5.3.2 Adverse events (AEs)

Summary tables for adverse events (AEs) will include only AEs that started or worsened during the on-treatment period, the *treatment-emergent* AEs.

The incidence of treatment-emergent adverse events (new or worsening from baseline) will be summarized by system organ class and or preferred term, severity (based on CTCAE grades), type of adverse event, relation to study treatment.

Serious adverse events, non-serious adverse events and adverse events leading to treatment discontinuations during the on-treatment period will be tabulated.

All deaths (on-treatment and post-treatment) will be summarized by system organ class and preferred term.

All AEs, deaths and serious adverse events (including those from the pre and post-treatment periods) will be listed and those collected during the post-treatment period will be flagged.

AEs will be assessed according to the Common Terminology Criteria for AEs (CTCAE version 4.03). AEs will be coded using the latest MedDRA terminology version during the time of data analyses.

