2. on-treatment period: from date of first administration of study treatment to 30 days after date of last actual administration of any study treatment (including start and stop date)
3. post-treatment period: starting at day 30+1 after last administration of study treatment.

Safety summaries (tables, figures) include only data from the on-treatment period with the exception of baseline data which will also be summarized where appropriate (e.g. change from baseline summaries). In addition, a separate summary for death including on-treatment and post-treatment deaths will be provided. In particular, summary tables for adverse events (AEs) will summarize only on-treatment events, with a start date during the on-treatment period (treatment-emergent AEs).

However, all safety data (including those from the pre- and post-treatment period) will be listed and those collected during the post-treatment period will be flagged.

Analysis Visit Windows

In order to summarize data collected over time (including unscheduled visits), the assessments will be time slotted. The following general rule will be applied in creating the assessment windows: If more than one assessment is done within the same time window, the assessment performed closest to the target date will be used. If 2 assessments within a time window are equidistant from the target date, then the earlier of the 2 assessments will be used. If there are multiple assessments on the same date, then the worst case will be used. Data from all assessments (scheduled and unscheduled), including multiple assessments, will be listed.

Analysis Visit windows

Assessment	Target day of assessment	Time Interval
Baseline	1	≤ Day 1
Week 4	28	Day 2 to day 42
Week 8	56	Day 43 to day 70
Week 12	84	Day 71 to day 98
Week 16	112	Day 99 to day 126
Week 20	140	Day 127 to day 154

Week 24	168	Day 155 to day 210
Week 36	252	Day 211 to day 294
Week 36+(12*k)	d=k*84+252, k=1,2,3,etc.	Day d-41 to day d+42

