2.8.1 Adverse events (AEs)

AE summaries will include all AEs occurring during on-treatment period. All AEs collected in the AE eCRF page will be listed along with the information collected on those AEs e.g. AE relationship to study drug, AE outcome etc. AEs starting during the post-treatment period will be flagged in the listings.

AEs will be summarized by number and percentage of subjects having at least one AE, having at least one AE in each primary system organ class (SOC) and for each preferred term (PT) using MedDRA coding. A subject with multiple occurrences of an AE will be counted only once in the respective AE category. A subject with multiple CTCAE grades for the same preferred term will be summarized under the maximum CTCAE grade recorded for the event. AE with missing CTCAE grade will be included in the 'All grades' column of the summary tables.

In AE summaries the primary system organ class will be presented alphabetically and the preferred terms will be sorted within primary SOC in descending frequency.

The following adverse event summaries will be produced by treatment; overview of adverse events and deaths (number and % of subjects who died), with any AE, any SAE, AEs by SOC and PT, summarized by relationship (all AEs and AEs related to study treatment), seriousness (SAEs and non-SAEs), leading to treatment discontinuation (drug withdrawn), leading to dose interruption/adjustment (dose increased or dose reduced), requiring additional therapy (concomitant medication or non-drug therapy) and leading to fatal outcome. In addition, a summary of serious and non-serious adverse events with number of occurrences will be produced (an occurrence is defined as >1 day between start and prior end date of record of same preferred term) as per EudraCT requirements.

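### The SAP's start-date rule counts as treatment-emergent a Grade 3/4 adverse event that arose between consent and first dose and only improved on drug

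*SAP*

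**What the plan says.** **Analysis rule in the SAP.** Section 2.1.1 states that "summary tables for adverse events (AEs) will summarize only on-treatment events, with a start date during the on-treatment period" and labels these events treatment-emergent. Section 2.8.1 repeats the rule without a filter on baseline or prior grade: "AE summaries will include all AEs occurring during on-treatment period".

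**Analysis rule in the protocol.** Section 10.5.3.2 says that the summary tables will "include only AEs that started or worsened during the on-treatment period". It then adds: "The incidence of treatment-emergent adverse events (new or worsening from baseline) will be summarized by system organ class". Both sentences ask for onset or worsening, not only for a date.

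**Recording rule in the protocol.** Section 8.1.1 splits one clinical event into several dated entries. On worsening: "If the event worsens the event should be reported a second time in the CRF noting the start date when the event worsens in toxicity". On improvement: "For grade 3 and 4 adverse events only, if improvement to a lower grade is determined a new entry for this event should be reported", again with its own start date.

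**Declared departures.** SAP Section 1 says the analysis follows Section 10 of the protocol, and SAP Section 4, on changes from the protocol, reads Not Applicable.

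**The concern.** If every entry marked the onset or worsening of an event, start date alone would be an adequate test. Here some entries mark an improvement. An entry opened because a pre-dose Grade 3/4 event eased after Day 1 has an on-treatment start date, so it passes the SAP test although the drug neither caused nor worsened the event.

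AE frequency and severity is a named secondary endpoint. Protocol 2.1 asks whether the dosing approach gives better tolerability than earlier trials, judged partly by AE incidence. With one arm, no concurrent control shares the error. The bias runs against the drug: it overstates toxicity.

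**Working it through.** The plan gives no figure to reproduce on this point. The check applies both rules to constructed record sequences and then converts misclassified patients into percentage points.

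**Inputs**
- AE collection starts at consent; screening runs from Day -28 to Day -1 (Protocol 8.1.1 and 4.1).
- Conditions present at consent go to the Medical History page (Protocol 8.1.1).
- A worsening event gets a second entry. An improving event gets one only if it is Grade 3 or 4 (Protocol 8.1.1).
- A patient counts once per AE category (SAP 2.8.1).
- Target N = 50 (SAP 1.1).

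**Sequences**

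| | Records | SAP start-date rule | Protocol rule |
|---|---|---|---|
| A | Grade 3 AE opened Day -10 after consent; eases to Grade 2 on Day 20 (new entry) | Counted, Grade 2 | Not counted |
| B | Grade 2 AE opened Day -10; eases to Grade 1 on Day 20 (no new entry) | Not counted | Not counted |
| C | Anemia present at consent; improves (Medical History) | Not counted | Not counted |
| D | Grade 2 AE opened Day -10; worsens to Grade 3 on Day 20 (new entry) | Counted, Grade 3 | Counted |
| E | As A, then back to Grade 3 on Day 60 | Counted, Grade 3 | Counted as worsened on treatment; not counted against baseline |

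Only A is a clear false count. E shows that the protocol's two phrases can disagree with each other when an event eases and returns.

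**Does anything downstream repair A?** The SAP's one record-joining rule (a gap of more than one day for the same preferred term, SAP 2.8.1) defines occurrences for the EudraCT count. It does not govern the patient counts by system organ class, preferred term, grade or relationship.

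**Can A happen?** Patients with hemoglobin above 6.5 and below 10 g/dL can enter. The label table in Protocol Appendix 6 puts Grade 3 anemia at 6.5 to below 8.0 g/dL (CTCAE 3.0; the trial uses 4.03). A fall after consent that needs transfusion is an AE, and the transfusion may itself bring the later improvement.

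**Size**
- Inflation in points = 100 × m / 50, where m is the number of affected patients with no other on-treatment record of that term.
- m = 1 gives 2.0 points, m = 2 gives 4.0, m = 3 gives 6.0 and m = 5 gives 10.0. The range of m is an assumption.
- If a share q of the affected patients also has a genuine on-treatment record, inflation = 100 × m × (1 − q) / 50, with m now counting all affected patients. Taking q = 0.793 for illustration (explained under the objection): m = 1 gives 100 × 0.207 / 50 = 0.4 points; m = 5 gives 100 × 1.035 / 50 = 2.1 points.

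**The case against.** The case for leaving this alone is that the affected group is small and the better comparison lies elsewhere.

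- **Most entry anemia is outside the mechanism.** It is medical history at consent, and the improvement rule applies only to Grade 3/4 AEs. This stands, and it limits the point to sequence A.
- **Genuine events will often mask the false one.** The appended label (section 4.4) says 79.3% of patients starting below 10 g/dL fall below 8.0 g/dL on treatment. If the same share of affected patients had a genuine anemia AE, one to five affected patients would add only 0.4 to 2.1 points. The direction of this argument stands. The figure is only illustrative, because it is a laboratory rate under label dosing and not an AE rate in this trial.
- **The laboratory tables are clean.** The CTC-grade and baseline-shift tables in SAP 2.8.3 are unaffected, and the label's anemia frequencies rest on laboratory values, so that is the like-for-like comparison. No decision criterion uses AE incidence. This stands, but it does not correct the AE tables, which serve a named endpoint.
- **The SAP already says it follows Section 10 of the protocol.** That does not rescue the text, because the SAP then states a different and more specific rule, which is the one that would be programmed.

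A reader might also infer that a patient already receiving transfusions would acquire an anemia AE with no change in need, because Protocol 8.1.1 treats a laboratory abnormality requiring transfusion as an AE. The documents do not support that. The same section defines an AE as something that appears, or worsens if pre-existing, after consent, and an unchanged need is neither.

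**Conclusion.** The SAP rule departs from the protocol without saying so and, combined with the recording rule, gives a wrong classification in one defined case. That case is a Grade 3/4 AE that arose or worsened between consent and the day before first dose and then improved on drug. It is not specific to anemia.

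The size is 2 percentage points of all-grade incidence per affected patient at N=50, and only where the patient has no other on-treatment record of that term. The number of such patients is not given. One to five is an assumption, and 10 points for five patients is what results if none of them has a genuine record. Because the false entry carries the lower grade, Grade 3/4 incidence is inflated by this route only when a Grade 4 event eases to Grade 3.

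It would be tempting to conclude that pre-treatment anemia in general will be reported as drug-emergent because every patient enters below 10 g/dL. Sequences B and C show that it will not. This is a modest, correctable error in the AE tables and does not threaten the trial's main results.

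**What to change.** In SAP 2.1.1 and 2.8.1:

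1. Restore the protocol's definition: an AE is treatment-emergent if it first appears on or after the first dose, or if its CTCAE grade rises above its grade at baseline.
2. Do not count an entry that only documents improvement of an AE already recorded before the first dose. Identify such entries by same preferred term, contiguous dates and lower grade.

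The comparator should be the baseline grade, as in the protocol, and not the highest pre-dose grade. With the latter, a Grade 4 event that eased to Grade 2 by baseline and rose to Grade 3 on drug would disappear from the tables. The same wording settles sequence E; if the sponsor prefers to count a relapse on treatment, the SAP should say so.

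If the start-date rule is kept instead, declare it in SAP Section 4.

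The cost is one extra derivation. No protocol change and no new data are needed.

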2.2 Analysis sets

2.2.1 Full Analysis Set

The Full Analysis Set (FAS) comprises all patients to whom study treatment (ruxolitinib) has been assigned and who received one dose of study treatment (ruxolitinib).

2.2.2 Safety set

The Safety set is the same as the FAS.

2.2.3 Per-Protocol set

The Per-Protocol Set (PPS) consists of a subset of the patients in the FAS who had no major protocol deviation.

The following major protocol deviations will lead to exclusion from the PPS:

- Patient with less than 12 years of age at screening
- Patients with unconfirmed diagnosis of PMF, PPV-MF or PET-MF, as reviewed by clinical team
- Patient without palpable splenomegaly or with a spleen length below 5 cm at baseline
- Patient with hemoglobin \geq than 10 g/dL at baseline
- Patient had prior treatment with any JAK1 or JAK2 inhibitor
- Patient has known hypersensitivity to ruxolitinib or other JAK1/JAK2 inhibitors, or to their excipients
- Treatment with another investigational medication or treated with an investigational medication within 30 days or 5 half-lives (whichever is longer) prior to the first dose of study drug
- Patient unable to comprehend or are unwilling to sign an ICF or Patient did not sign ICF or amended ICF
- Concomitant use of another JAK inhibitor
- Use of investigational medication not approved for any indication within 30 days or 5 half-lives, whichever is longer, prior to the first dose of study drug and until treatment discontinuation
- Use of hydroxyurea, interferon, thalidomide, busulfan, lenalidomide, or anagrelide on Day 1 of ruxolitinib therapy and at any time during participation in the study
- Use of potent CYP3A4 inducers in combination with ruxolitinib

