5.2 Inclusion criteria

Patients eligible for inclusion in this study have to meet **all** of the following criteria:

Written informed consent must be obtained prior to any screening procedures.

1. Male or female patients aged ≥ 18 years of age.
2. Patients must be diagnosed with PMF, according to the 2016 revised International Standard Criteria (Arber et al. 2016), PPV MF or PET-MF (Barosi 2008), irrespective of JAK2 mutation status.
3. Patients with palpable splenomegaly that is equal to or greater than 5 cm below the left costal margin.
4. Patients with a hemoglobin less than 10 g/dL
5. Patients with a history of transfusions must have a documented transfusion record in the previous 12 weeks to baseline.
6. Patients with an ECOG performance status of 0, 1, or 2.
7. Patients with a peripheral blood blast percentage count of $< 10\%$.
8. Patients must have recovered or stabilized sufficiently from any adverse drug reactions associated with prior treatments before beginning treatment with ruxolitinib.

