7.1.2.1 Eligibility screening

Patients must meet all inclusion ([Section 5.2](#)) and none of the exclusion ([Section 5.3](#)) criteria during the Screening phase in order to be eligible to proceed to the Treatment Phase of the study. Patient eligibility will be confirmed by using the following processes:

[figure not shown]
- Investigative staff will capture patient eligibility within the source documents maintained at the site,
- All screening assessment results must be received and reviewed by the investigator/designee to be within protocol required parameters before the patient starts study treatment,

Following registering in the IRT for screening, patient eligibility will be checked by the Sponsor once all screening procedures are completed. The eligibility check form will be sent from the site to the Sponsor either via fax or email for evaluation. Upon confirmation of eligibility, the Sponsor will return the signed eligibility check form via fax or email to the site.

The investigator site will then contact the IRT to be allowed to assign treatment to the patient. Please refer and comply with detailed guidelines in the IRT manual.

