10.1.3 Per-Protocol set

The Per-Protocol Set (PPS) consists of a subset of the patients in the FAS who had no major protocol deviation.

Any protocol deviations potentially leading to exclusion from the PPS will be specified in the study Statistical Analysis Plan (SAP). This population will be used as supportive analyses for the primary efficacy endpoint.

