2.5.4 Supportive and Sensitivity analyses

The primary analysis (as described in Section 2.5.2) will also be repeated on the PPS. Furthermore, the primary endpoint will be analyzed on patients with non-missing spleen length at both baseline and Week 24. Proportion of patients achieving a 50% reduction in spleen length

at any time during the study will also be reported along with corresponding exact 95% confidence interval using Clopper and Pearson exact method.

IWG-MRT response criteria will also be used to analyze spleen length response rate at Week 24. Response as per IWG-MRT criteria is defined as follows:

- A baseline splenomegaly that is palpable at 5-10 cm, below the LCM at baseline, becomes not palpable, post-baseline or
- A baseline splenomegaly that is palpable at >10 cm at baseline, below the LCM, decreases by $\geq 50\%$, post-baseline
- A baseline splenomegaly that is palpable at <5 cm at baseline, below the LCM, is not eligible for spleen response

Patients meeting response criteria as per above definition will be considered as responders or else will be non-responders. The point estimate of the proportion of responders along with corresponding exact 95% confidence interval using Clopper and Pearson exact method will be presented at Week 24. The same analysis will be repeated for proportion of responders as per IWG-MRT response criteria for spleen at any time during the study.

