2.14 Interim analysis

No formal interim analysis is planned for this trial.

The primary analysis will be performed after all patients have completed Week 24 or discontinued prior to Week 24. Any other interim updates may be provided to fulfill regulatory obligations to comply with post-approval commitments, or for publication purposes.

The final analysis will occur at the end of the study. All available data from all patients will be analyzed and summarized in a final CSR.

3 Sample size calculation

Approximately 50 patients will be enrolled in this study. Success at Week 24 will be declared if the following criteria are met:

- a. Observed proportion of patients with $\geq 50\%$ reduction in spleen length at Week 24 $\geq 25\%$
- b. Probability of true response rate $\leq 15\%$ (considered not clinically meaningful) is less than 10%

With 50 patients, criteria 'a' and 'b' will be met if the observed responder rate is $\geq 25\%$, i.e. if at least 13 patients out of 50 patients have a response at Week 24.

Sample Size	No. of responders	Observed responder rate (%)	Probability of true responder rate $\leq 15\%$
N=50	11	22	0.1014
	12	24	0.0520
	13	26	0.0243

	14	28	0.0104
	15	30	0.0041
	16	32	0.0015

The operating characteristics of the design are presented in the table below. This table shows the probability for positive conclusion (i.e. success criteria met at the end of the study) under different true responder rates. When the true responder rate at Week 24 is $\leq 15\%$, the probability of positive conclusion is $\leq 10\%$ (false success rate). The probability of success is $> 90\%$ when the true responder rate at Week 24 is 35%.

Sample Size	True responder rate (%)	Probability of positive conclusion
N=50	15	0.0301
	20	0.1861
	25	0.4890
	30	0.7771
	35	0.9339
	40	0.9867
	45	0.9982
	50	0.9998

4 Change to protocol specified analyses

Not Applicable.

5 Appendix

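### The SAP's per-protocol exclusion list sets the age limit at 12 where the protocol requires 18; secondarily, it covers no ruxolitinib dosing breach

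*SAP*

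**What the plan says.** **Age.** Protocol 5.2, inclusion criterion 1, reads "Male or female patients aged" 18 or over. SAP 2.2.3 introduces its list with "The following major protocol deviations will lead to exclusion from the PPS", and the first item is "Patient with less than 12 years of age at screening". SAP section 4, "Change to protocol specified analyses", is marked as not applicable.

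**Who defines the list.** Protocol 10.1.3 defines the PPS as FAS patients with no major deviation and leaves the excluding deviations to the SAP. Of the PPS it says: "This population will be used as supportive analyses for the primary efficacy endpoint". SAP 2.5.4 states that the primary analysis "will also be repeated on the PPS".

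**What the list covers.** It has 12 items. Eight concern eligibility, consent or prior treatment. The last four reach into the treatment period: another JAK inhibitor, unapproved investigational drugs, named prohibited drugs such as hydroxyurea, and potent CYP3A4 inducers. No item concerns ruxolitinib dose, reduction, interruption or titration.

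**What the protocol says about dosing.** Section 6.3.1.1 permits no departure from the interruptions and reductions it makes mandatory, and says Table 6-2 is the reference for identifying a deviation. Section 6.3.3 bars restarting after an interruption of more than 8 weeks, with a 12-week allowance for splenectomy. Section 7.1.4 names that limit as a deviation from the dose regimen, next to use of prohibited treatment.

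**The concern.** The age item contradicts the eligibility criterion it is meant to enforce. As written, a patient aged 12 to 17 treated in error would breach inclusion criterion 1 and still count as per protocol.

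The dosing gap concerns what the PPS repeat is for. The trial studies a starting dose with a titration scheme. A per-protocol repeat that removes patients for taking a prohibited drug, but not for ruxolitinib dosing that broke a mandatory rule, answers only part of the adherence question. The other analyses in SAP 2.5.4 (non-missing data, response at any time, IWG-MRT response) do not fill the gap. Deviations are tabulated under SAP 2.3.1 and dose changes summarised under SAP 2.4.1, but neither is linked to response.

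**Working it through.** **1. Age: the passages side by side.** Protocol 5.2 sets a minimum of 18. The SAP 2.2.3 exclusion starts below 12. Ages 12 to 17 fall between the two, and SAP section 4 offers no explanation. Against any practical effect, protocol 7.1.2.1 says "patient eligibility will be checked by the Sponsor once all screening procedures are completed", and protocol 1.1 puts the median age at diagnosis at about 65.

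**2. Dosing: is there another route out of the PPS?** SAP 2.2.3 opens with the general phrase about major deviations, then lists items. Neither document defines major in any other way. SAP 2.3.1 cites a Data Handling Plan, which is not among the documents, but only for the categories used in a tabulation. Protocol 10.1.3 assigns PPS exclusions to the SAP. The natural reading is therefore that patients with a dosing breach stay in.

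**3. The rule that the PPS repeats.** SAP 2.5.2 requires (a) an observed rate of at least 25% and (b) P(true rate <= 15%) below 0.10. SAP 5.6.1 gives the prior Beta(1/3, 1), so the posterior for y responders among n is Beta(1/3 + y, 1 + n - y). For 13/50, P(p <= 0.15) = 0.0243, which reproduces the SAP figure. P(at least 13 of 50) is 0.0301 at a true rate of 15% and 0.9339 at 35%, also as stated.

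**4. How far could a few exclusions move the PPS result?** The documents give no dosing-deviation rate. Purely as an illustration, assume that 1 to 5 of 50 patients are excluded. In the worst case all k excluded patients are responders. Criterion (a) then fails when (y - k)/(50 - k) < 0.25, that is, when k > (4y - 50)/3.

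| FAS responders of 50 | Smallest k that fails (a) | PPS result | Posterior P(p <= 15%) |
|---|---|---|---|
| 13 | 1 | 12/49 = 24.5% | 0.0452 |
| 14 | 3 | 11/47 = 23.4% | 0.0704 |
| 15 | 4 | 11/46 = 23.9% | 0.0615 |
| 16 | 5 | 11/45 = 24.4% | 0.0535 |
| 17 | 7 | 10/43 = 23.3% | 0.0836 |

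In each row it is criterion (a) that fails; (b) is still met. From 17/50 upward, losing five responders changes neither criterion (12/45 = 26.7%, posterior 0.0242). An FAS count of 13 to 16 has probability 0.461, 0.323 and 0.143 at true rates of 30%, 35% and 40%.

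The other extreme excludes only non-responders, which raises the rate: 13/45 = 28.9% (+2.9 points) and 16/45 = 35.6% (+3.6 points). A near miss can then turn into a PPS pass: 12/50 = 24.0% fails (a), while 12/48 = 25.0% (posterior 0.0390) meets both. For FAS counts of 13 to 16, the full range of movement is -8.2 points (13/50 to 8/45 = 17.8%) to +3.6 points. If excluded patients respond at the FAS rate, the expected change is zero.

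**5. The neutrophil hold.** 500/uL equals 0.5 x 10^9/L. The 6.3.1.1 text holds dosing at or below that value; Table 6-2 holds it only below. A count of exactly 500/uL is therefore a mandatory hold under one and not under the other.

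**The case against.** The age item looks like a slip with no shown effect. That stands as to consequence. It does not make the item right: the SAP chose to list age, and the cut-off it gives is not the protocol's.

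On dosing the opposing case is stronger. Protocol 10.1.3 leaves the choice to the SAP, and the SAP made it. The protocol calls a Table 6-2 breach a deviation but never a major one. Section 7.1.4 concerns stopping treatment, not analysis sets. The list is selective elsewhere too, omitting the ECOG, blast, neutrophil, platelet, renal and hepatic criteria. Nor does it say that it is exhaustive. Finally, excluding patients for conduct driven by blood counts, in a single arm, is selection on something that may be related to spleen response. All of this stands, and it keeps the dosing point minor. It does not remove the inconsistency of excluding one kind of on-treatment breach and not another that the protocol expressly forbids.

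A reader might infer three stronger things. One is that the primary result is at risk; it is not, because that analysis uses the FAS. Another is that omitting dosing breaks a protocol rule; no rule requires its inclusion. The third is that the PPS repeat will mislead; the documents give no breach rate from which to judge that.

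**Conclusion.** The age limit in SAP 2.2.3 is an error and should be corrected. It changes no number unless a patient aged 12 to 17 was treated, which is unlikely.

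The dosing omission is a real but minor gap, confined to a supportive analysis. It rests on reading the 12 items as the operative list, which is the natural reading but not a certain one. Its effect is unknown. The figures above are bounds under an assumed 1 to 5 exclusions, not estimates. They show only that the PPS repeat could disagree with the FAS result when the FAS count is close to 13. The FAS analysis and its decision rule are unaffected by either point.

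**What to change.** 1. In SAP 2.2.3, change the age item from under 12 to under 18.
2. Before database lock, add two PPS exclusions to SAP 2.2.3, limited to breaches before the Week 24 spleen assessment: (i) a mandatory Table 6-2 reduction or interruption that was not applied; (ii) dosing resumed after an interruption longer than the protocol 6.3.3 limit, keeping its splenectomy exception.
3. State that dose changes the protocol requires or permits are not deviations. These include inhibitor adjustments under 6.4.2, re-escalation under 6.3.5 and the optional steps in 6.2.3.
4. Report the number excluded and their response status.
5. Before applying (i), reconcile the neutrophil hold in the 6.3.1.1 text with Table 6-2. Which wording should prevail is for the sponsor.

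The cost is SAP wording and some programming from dosing and laboratory data already collected. The downside is a slightly smaller PPS, selected partly on post-baseline conduct, so it must remain supportive.
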